**Table 3. Performance indicators at health facility level.**

Indicator	Numerator	Denominator	Data Source	Breakdown	Frequency of collection
1. Number of hypertensive patients enrolled in the Cardiovascular	Number of hypertensive patients enrolled in the CVRP	NA	Billing and electronic clinical records	Cardiovascular risk level (low, medium, high), grade of hypertension (I, II, III)	Monthly

Risk Program (CVRP)				II, resistant), sex, age, pharmacological treatment (yes, no), co-morbidities, complications, health care setting	
2. Prevalence of diagnosed hypertension in Metrosalud's catchment area	Number of hypertensive patients enrolled in the CVRP	Total population for whom Metrosalud is responsible in the studied Commune	For the numerator: Billing and electronic clinical records  For the denominator : Database of the Subsidized Regime and non-insured assigned population	Cardiovascular risk level (low, medium, high), grade of hypertension (I, II, resistant), sex, age, pharmacological treatment (yes, no), co-morbidities, complications, health care setting	Quarterly
3. Ratio of prevalence of diagnosed hypertension to the expected prevalence of hypertension in Metrosalud's catchment area	Prevalence of diagnosed hypertension in Metrosalud's catchment area	Expected prevalence of hypertension in the population for whom Metrosalud is responsible in the catchment area	For the numerator: Billing and electronic clinical records  For the denominator : Survey "Gaps in hypertension care and control in two Communes".	Sex, age, health care setting	Quarterly
4. New hypertensive	Total number of new	NA	Billing and electronic	Cardiovascular risk level (low,	Monthly

patients enrolled in the CVRP	hypertensive patients enrolled in the CVRP during a month		clinical records	medium, high), grade of hypertension (I, II, resistant), sex, age, pharmacological treatment (yes, no), co-morbidities, complications, health care setting	
5. Cardiovascular risk assessment	Hypertensive patients with a recorded cardiovascular assessment in the last 1 year	Number of hypertensive patients enrolled in the CVRP	Billing and electronic clinical records	Cardiovascular risk level (low, medium, high), grade of hypertension (I, II, resistant), sex, age, pharmacological treatment (yes, no), co-morbidities, complications, health care setting	Annual
6. High calculated cardiovascular risk	Hypertensive patients with calculated cardiovascular disease risk $\geq 20\%$ in 10 years and systolic blood pressure (BP) $\geq 140/90$ mm Hg at last BP measurement during the last year.	Number of hypertensive patients enrolled in the CVRP	Billing and electronic clinical records	Pharmacological treatment (yes, no), sex, age	Biannual
7. Prevalence of controlled	Hypertensive patients with documented	Number of hypertensive patients	Billing and electronic clinical	Pharmacological treatment (yes,	Biannual

hypertension	systolic BP <140 mm Hg and diastolic BP <90 mm Hg in at the most recent BP measurement during the last year.	enrolled in the CVRP	records	no), sex, age	
8. Prevalence of controlled hypertension 6 months after enrolment in the CVRP	Hypertensive patients who started treatment 6 months before the reporting trimester and have systolic BP <140 mm Hg and diastolic BP <90 mm Hg at follow-up visit during the reporting trimester	Number of hypertensive patients enrolled in the CVRP who started treatment 6 months before the reporting trimester	Electronic clinical records	Sex, age, pharmacological treatment (yes, no), non-pharmacological treatment (yes, no)	Quarterly
9. Uncontrolled hypertension in patients with cardiovascular disease, renal disease or diabetes	Hypertensive patients diagnosed $\geq 6$ months before the start of the reporting period, and cardiovascular disease, renal disease, or diabetes mellitus, who had systolic BP $\geq 140$ mm Hg or diastolic BP $\geq 90$ mm Hg at the most recent BP measurement during the last	Number of hypertensive patients enrolled in the CVRP $\geq 6$ months before the start of the reporting period	Electronic clinical records	Pharmacological treatment (yes, no), sex, age	Quarterly

	year				
10. Uncontrolled hypertension 2	Hypertensive patients diagnosed $\geq 6$ months before the start of the reporting period who had systolic BP $\geq 160$ mm Hg or diastolic BP $\geq 100$ mm Hg at the most recent BP measurement during the last year	Number of hypertensive patients enrolled in the CVRP $\geq 6$ months before the start of the reporting period	Electronic clinical records	Pharmacological treatment (yes, no), sex, age	Quarterly
11. Resistant hypertension	Hypertensive patients diagnosed $\geq 6$ months before the start of the reporting period and who are treated with three or more antihypertensive drugs, who had systolic BP $\geq 160$ mm Hg or diastolic BP $\geq 100$ mm Hg at the most recent BP measurement during the last year	Number of hypertensive patients enrolled in the CVRP $\geq 6$ months before the start of the reporting period	Electronic clinical records	Sex, age	Quarterly
12. Six-monthly control of blood pressure among people started on pharmacological treatment for	Number of patients started on pharmacological treatment of hypertension during the	Number of patients started on pharmacological treatment of hypertension	Electronic clinical records	Sex, age	Quarterly

hypertension	quarter that ended 6 months before, with controlled blood pressure (SBP<140 and DBP<90) at the last clinical visit in the most recent quarter (just before the reporting quarter)	during the quarter that ended 6 months before			
--------------	---	---	--	--	--

The indicators for measuring the process implementation of different components of the intervention are listed in Table 4.

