#### 4.1.2 Study population, Sampling, Sample Size and Power

The study communes are chosen purposively according to the following inclusion criteria: urban setting; low and/or middle-income population; typical functioning of the national health system; commitment of the main actors in health care provision in the area to develop improvement programmes based on research results.

All health structures and their catchment population aged 35 years or older will be involved in the study.

For the endline survey, the same methodology applied for the aforementioned baseline survey will be used. Expecting a baseline hypertension control gap of 45%, a sample of 280 hypertensive individuals 35 years or older is required to estimate a 10% difference in the magnitude of the control gap in the intervention vs the control area at endline, with power 0.75 and alfa 0.10. Given a 40% prevalence of hypertension (see 4.1.4 for definitions) in individuals aged 35 years or older, screening around 700 individuals 35 years or older in each Commune, will allow to find the needed number of hypertensive individuals. This is increased to 1150 individuals, assuming a percentage of non-response of 10% and a design effect of 1.5, given the sampling strategy outlined below. From a sampling frame containing the addresses of all homes of the Communes, provided by the Planning Office of the Municipality, a stratified one-stage cluster sampling will be implemented in order to obtain a representative sample of the population aged 35 years or older living in the selected Communes. Considering that in households there are on average 1.5 individuals 35 years old or older, 765 households will be included in each Commune. In each Commune, clusters of 15 contiguous households will be defined with the help of maps and 51 clusters will be selected by randomly sampling each neighbourhood of the Commune. The number of randomly selected clusters in each neighbourhood will be proportional to the neighbourhood size (weights assigned to each neighbourhood according to its total number of households). The module for complex samples of the Statistical Package for Social Sciences (SPSS) V.24 (SPSS Inc., Chicago, IL, USA) will be used. Door to door visits to every single household of each selected cluster will be made by a group of trained surveyors. All identified eligible consenting individuals aged 35 years or older will be interviewed.

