###### *4.2.2.1.2. Data collection at health services:*

**Data sources:** databases of the Subsidized Regimen and of the non-insured poor population, electronic clinical and billing records of Metrosalud, registers of the “Healthy Hearts” service (Annex 3, 4 and 5), exit-interview forms (Annex 6), audit form (Annex 7, an adapted format for the audit of clinical records in use at Metrosalud), lists of participants and minutes of meetings and training activities, test results during trainings, registers and inventory at the pharmacy service, and report of activities by health professionals.

Besides the data explicitly mentioned in the annexes and tables of this protocol, we will collect the data mentioned below.

**Data extracted from the databases of the Subsidized Regimen and of the non-insured poor population (data will be extracted either in the intervention and in the control commune):**

- the total adult population (by sex, age, place of living and health insurance affiliation) for whom Metrosalud is responsible in the catchment area (target population).

**Data extracted from the billing and electronic clinical records of Metrosalud (data will be extracted either in the intervention and in the control commune):**

- number of patients enrolled in the CVRP.
- regarding patients enrolled in the CVRP: sex, age, frequency and results of cardiovascular risk assessment, prescribed pharmacological/non-pharmacological treatment, BP figures, major comorbidities and complications.
- number of patients who have missed a hypertension-related appointment

**4.2.3 Qualitative component** The qualitative component will be carried out by a social scientist with previous experience in the use of qualitative methods, under the supervision of a senior sociologist from the Latin American Network for Multidisciplinary Research on Chronic Diseases with expertise in implementation fidelity.

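### As written in Table 3, indicator 3 compares a diagnosed prevalence over Metrosalud's total or adult population with an expected prevalence from people aged 35 or older, so the overall ratio understates diagnostic coverage

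*Combined protocol and SAP*

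**What the plan says.** Table 3 (section 4.3.1) defines indicator 2, the prevalence of diagnosed hypertension, as the "Number of hypertensive patients enrolled in the CVRP" over the "Total population for whom Metrosalud is responsible in the studied Commune". Neither part carries an age limit. Section 4.2.2.1.2, which lists what will be drawn from the Subsidized Regimen and non-insured databases, describes that population as "the total adult population (by sex, age, place of living and health insurance affiliation) for whom Metrosalud is responsible". It is adult, and again not limited to 35 or older.

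Indicator 3 is a quarterly ratio. Its numerator is indicator 2. Its denominator is the "Expected prevalence of hypertension in the population for whom Metrosalud is responsible in the catchment area", and the data source given for that denominator is the survey "Gaps in hypertension care and control in two Communes". Section 4.1.2, which applies the baseline methodology to the endline survey, says that the sampling is meant to give "a representative sample of the population aged 35 years or older living in the selected Communes".

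Age is listed as a breakdown for both indicators, without bands or a lower limit. Section 4.3.1 says that the Table 3 indicators serve both to monitor implementation and to measure effects at health service level. They are to be measured in both communes from baseline to endline.

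**The concern.** A ratio of diagnosed to expected prevalence measures coverage only if both prevalences refer to the same people. Here the base of the numerator prevalence includes people under 35, who add many to the population count and, in all likelihood, few hypertensive patients. The expected prevalence comes from a survey that has no one under 35 in it and cannot supply a figure for them. Table 3 gives no rule for bridging the two.

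Indicator 3 is the only item in Table 3 that sets diagnosed hypertension against expected hypertension, so it is where a reader will look for diagnostic coverage at facility level during implementation. If it is calculated as written, coverage looks worse than it is and gains look smaller than they are. Two communes with equal coverage but different age structures would also show different values.

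**Working it through.** The documents state no value or target for indicator 3, so there is no figure to reproduce. The check is algebra.

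**Notation**
- s: share of Metrosalud's denominator population aged 35 or older. Not in the documents.
- p: prevalence of hypertension at 35 or older. It is 43.4% in the 2016 survey (section 1.2) and 40% as the planning value (section 4.1.2).
- c: share of hypertensive people aged 35 or older who are diagnosed and enrolled in the Cardiovascular Risk Program (CVRP).
- q: enrolled hypertensive patients under 35 divided by the population under 35. Not in the documents.

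**Formula**
- Indicator 2 = s·c·p + (1 − s)·q
- Indicator 3 = indicator 2 / p = s·c + (1 − s)·q/p

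At full diagnosis and enrolment (c = 1) this is s + (1 − s)·q/p. It equals 1 only if s = 1 or q = p. With q = 0 it equals s, whatever p is.

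**Assumed range for s.** The only related figure in the documents is an average of 1.5 people aged 35 or older per household (section 4.1.2). The household sizes below are assumptions, as is applying a commune-wide household average to Metrosalud's population.
- All-ages reading, 3 to 4 persons per household: s = 1.5/4 to 1.5/3 = 0.375 to 0.50.
- Adult reading, 2 to 2.5 adults per household: s = 1.5/2.5 to 1.5/2 = 0.60 to 0.75.

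**Indicator 3 at full diagnosis, p = 43.4%, q assumed**

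| Reading | s | q = 0 | q = 5% | q = 10% |
|---|---|---|---|---|
| All ages | 0.375 | 0.375 | 0.447 | 0.519 |
| All ages | 0.50 | 0.500 | 0.558 | 0.615 |
| Adult | 0.60 | 0.600 | 0.646 | 0.692 |
| Adult | 0.75 | 0.750 | 0.779 | 0.808 |

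With p = 40% and q = 10%, the four values are 0.531, 0.625, 0.700 and 0.812, so the choice of p hardly matters. To reach 0.90 with s = 0.60 and p = 43.4%, q would have to be (0.90 − 0.60)/0.40 × 0.434, or about 33%.

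**Absolute change.** A rise in c of 0.10 shows as 0.10·s: 0.05 at s = 0.50, and 0.06 at s = 0.60.

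**Comparison between communes.** With equal c and q = 0, assumed shares of 0.50 and 0.55 give ratios that differ by 0.55/0.50 = 1.10, or 10% in relative terms.

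**Relative trend within a commune.** With q = 0 and s stable, s cancels from the ratio of two quarters. With a small q it cancels approximately.

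**Matched base.** With CVRP patients and population both limited to 35 or older, indicator 3 = c·p/p = c, and full diagnosis reads 1.00.

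**The case against.** The strongest reply is that the survey is named only as a data source. By definition, both prevalences in indicator 3 refer to the population for whom Metrosalud is responsible, and nothing says that the crude survey figure goes in unadjusted. The plan also leans towards a 35-plus base: sections 1.2 and 3 address the intervention to people aged 35 or older, section 4.1.2 involves the catchment population of that age, and section 4.2.2.1.2 calls its extract the target population. If that base was meant, the mismatch disappears.

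This makes the intention plausible but does not settle the rule. Table 3 says total, section 4.2.2.1.2 says adult, and no restriction or standardisation is given. The survey could not support an expected prevalence for under-35s in any case. An analyst who follows the text gets the mismatched ratio.

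The age breakdown helps in part, because strata aged 35 or older can be matched and can reach 1. It does not repair the overall figure. Section 8.1 says that only aggregate data will be extracted from the records and population databases, so without a cut at 35 a later repair may not be possible.

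Two stronger readings are tempting and should be resisted.
- A reader might infer that the indicator misses its own target of 1. The plan states no such target.
- A reader might take the 63.3% awareness in the 2016 survey (100% − 36.7%), multiply it by s, and call the result the expected current reading. The documents do not support this. Awareness is self-reported by residents in a population survey, while CVRP enrolment belongs to one provider's programme.

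**Conclusion.** The point holds for the overall ratio as Table 3 is written. Indicator 3 understates diagnostic coverage by roughly the factor s whenever enrolled prevalence under 35 is lower than prevalence at 35 or older. The direction follows from the definitions. The size rests on assumptions about s and q: full diagnosis would read about 0.6 to 0.8 on the adult reading and about 0.4 to 0.6 on the all-ages reading.

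The level and the absolute change are affected, and so is any comparison between communes whose age structures differ. Whether these two communes differ is unknown: section 4.1.1 reports socio-economic similarity and the sex split but no age distribution.

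A reader might infer that the evaluation of the diagnosis gap is compromised. It is not. That gap is a main outcome in Table 1, measured by the population surveys and compared by difference in differences, and indicator 3 does not enter it. Relative trends within a commune are also largely preserved if the age structure is stable. This is a defect in one monitoring indicator, worth correcting because the correction is nearly free.

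**What to change.** In Table 3:
- Restrict the CVRP count and the Metrosalud population used for indicator 3, and the version of indicator 2 that feeds it, to people aged 35 or older, in line with section 4.1.2.
- State that the expected prevalence is the survey prevalence standardised to the age and sex distribution of Metrosalud's population aged 35 or older.

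In section 4.2.2.1.2, specify that the aggregate extracts from the population databases and the clinical records are cut at age 35, with the age and sex groups needed for the standardisation.

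The cost is wording. Age and sex are already listed for the population and CVRP extracts, so no new data source is needed. Patients under 35 drop out of this one ratio. They can still be counted in indicator 1 and in an all-ages version of indicator 2, if the team wants to keep one.

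### Table 3, indicator 7 has no minimum enrolment time, so recent case-finding and missing BP readings are mixed with true control when the communes are compared

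*Combined protocol and SAP*

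**What the plan says.** All references are to the combined protocol and SAP.

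- **Indicator 7 (Table 3).** The numerator is patients with a documented "systolic BP <140 mm Hg and diastolic BP <90 mm Hg in at the most recent BP measurement" in the last year. The denominator is every hypertensive patient "enrolled in the CVRP". There is no minimum time since diagnosis or enrolment. The breakdown is by drug treatment, sex and age, not by time since enrolment.
- **Indicators 9, 10 and 11.** Numerator and denominator are limited to patients diagnosed or enrolled at least 6 "months before the start of the reporting period". Indicator 9 counts only patients with cardiovascular disease, renal disease or diabetes in its numerator; 10 and 11 use a 160/100 threshold.
- **Indicators 8 and 12.** These report control below 140/90 in starter cohorts. The denominator of indicator 8 is "Number of hypertensive patients enrolled in the CVRP who started treatment 6 months before the reporting trimester".
- **Indicator 4.** This counts new "hypertensive patients enrolled in the CVRP during a month", without their control status.
- **Case-finding.** Increased detection is a secondary objective (section 2). The Healthy Hearts service passes all newly diagnosed patients to the CVRP and follows up missed visits (section 4.2.1, A.2), and the community group screens in public places (C.2). The control commune receives standard care (section 4.2).
- **Use.** Section 4.3.1 has the Table 3 indicators measured in both communes at baseline, during implementation and at endline, to show results and effects at health service level.
- **Extraction.** Only aggregate data are taken from the Metrosalud records (section 8.1).

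**The concern.** A patient found by screening enters the CVRP because blood pressure was at or above 140/90 on serial measurement (Table 4, indicators 17 and 20). On entry that patient therefore fails indicator 7's threshold, yet is counted in its denominator at once. If the intervention commune has a larger share of such patients than the control commune, the two values of indicator 7 differ through case mix alone.

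A second feature acts on the same number. An enrolled patient with no reading in the year is in the denominator but cannot be in the numerator. Active recall in the intervention commune should reduce that group, which would raise indicator 7 there without any change in blood pressure.

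Indicator 7 is the only Table 3 measure of control below 140/90 across all CVRP patients, and no indicator gives that rate for the established cohort. What is at stake is how the health-service results are read: one figure combines true control, case mix and recording.

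**Working it through.** The plan states no target, sample size or power for indicator 7, so there is no figure of its own to reproduce.

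**Inputs**

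- Established control, C_est = 1 − 0.41 = 0.59. The 41% uncontrolled among aware hypertensives is from the 2016 survey (section 1.2), used here as a proxy for CVRP patients.
- Duration of the intervention: 24 months (section 3).
- Enrolment growth over that time: 20% or 30% of baseline enrolment (assumed).
- Control among patients enrolled under 6 months, C_new: 0.20 to 0.40 (assumed).
- Growth is even over time, and joiners of 6 months or more reach 0.59 (assumed).

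**Formula**

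Indicator 7 = (1 − s) × C_est + s × C_new, where s is the share of the denominator enrolled under 6 months. The fall is s × (C_est − C_new).

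**Even growth.** One quarter of the growth (6 of 24 months) is recent at endline.

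- 20% growth, recent part 0.05, total 1.20:
  - (0.59 × 1.15 + 0.05 × 0.20) / 1.20 = 57.4%, a fall of 1.6 points
  - (0.59 × 1.15 + 0.05 × 0.40) / 1.20 = 58.2%, a fall of 0.8 points
- 30% growth, recent part 0.075, total 1.30:
  - (0.59 × 1.225 + 0.075 × 0.20) / 1.30 = 56.75%, a fall of about 2.3 points
  - (0.59 × 1.225 + 0.075 × 0.40) / 1.30 = 57.9%, a fall of 1.1 points

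**Extreme case: all growth in the last 6 months**

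- 20%: (0.59 + 0.20 × 0.20) / 1.20 = 52.5%; (0.59 + 0.20 × 0.40) / 1.20 = 55.8%. Fall 3.2 to 6.5 points.
- 30%: (0.59 + 0.30 × 0.20) / 1.30 = 50.0%; (0.59 + 0.30 × 0.40) / 1.30 = 54.6%. Fall 4.4 to 9.0 points.

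**Direction.** If recent enrollees were controlled at 59%, the change would be zero. At 70% it would reverse: with s = 0.05 / 1.20 = 0.042, the indicator rises by 0.042 × 0.11, about 0.5 points.

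**Missing readings.** Section 1.2 gives 15% of aware hypertensives with no follow-up consultation in the year. Taking that as the no-reading share, with equal control in those patients (both assumed), the starting value is 0.59 × 0.85 = 50.2%. The fall under even 20% growth is then 0.042 × (0.502 − 0.20) = 1.3 points, or 0.042 × (0.502 − 0.40) = 0.4 points. In the other direction, if recall cut the no-reading share by 2 points and those patients were controlled at 59%, indicator 7 would rise by 2 × 0.59, about 1.2 points.

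**After the change.** With both numerator and denominator restricted to at least 6 months' enrolment, s = 0 and the effect of recent enrolment is zero under these assumptions.

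**The case against.** The strongest case against has four parts.

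- **Other indicators show the problem.** Indicators 1 and 4 report total and new enrolment, 8 and 12 give control in starter cohorts, and indicator 7 is split by drug treatment. Together these would reveal that the case mix had shifted, and that much stands. They cannot rebuild the established-cohort rate. Indicator 4 carries no control status, indicators 8 and 12 describe cohorts that started about six months earlier, and a patient who began drugs last week falls in the treated group.
- **The crude rate is legitimate.** Control among everyone enrolled is a sensible monitoring measure. This stands, and is why indicator 7 should be kept.
- **The size is uncertain.** The 59% is from a community survey, not CVRP records. The survey definition of control in section 4.1.4 allows 150/90 from age 60, while indicator 7 uses 140/90 at all ages; the plan does not say which definition the 2016 figure used. Both this and unmeasured patients point to a lower starting rate and a smaller effect. This stands.
- **Nothing formal depends on it.** Difference-in-difference is specified for the main outcomes, which are the Table 1 population gaps, and no test of indicator 7 is planned. This stands.

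A reader might go further and infer that indicator 7 is the main facility-level control measure and is biased against the intervention by 3 to 9 points. The documents do not support that. Table 3 ranks no indicator. Falls of that size need all enrolment growth to come in the last 6 months, whereas the intervention runs for 24. The net direction is also not established, because recall of non-attenders pulls the other way.

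**Conclusion.** The point holds in a limited form. Indicator 7 lacks the 6-month rule that indicators 9 to 11 use, and no Table 3 indicator shows control below 140/90 in established CVRP patients. Recent case-finding pushes the indicator down in the intervention commune only if recent enrollees are less often controlled than established ones. That is likely from the way they are detected, but the documents give no rate.

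Under the stated assumptions the downward effect is about 0.8 to 1.6 points with 20% growth and 1.1 to 2.3 points with 30%. A modest fall in the share without a reading could offset it, and a true gain in control could outweigh it. Patients who remain uncontrolled after 6 months are a real result and not part of this artefact.

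This is a cheap improvement to a health-service indicator. The Table 1 population outcomes are unaffected.

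**What to change.** - Keep indicator 7 as it is.
- Add a version with numerator and denominator both restricted to patients enrolled at least 6 months before the reporting period, as in the denominators of indicators 9 to 11. Use this version for the comparison between communes.
- Add a separate line for the share of enrolled patients with no BP reading in the last year.
- Extract both identically in the two communes, from baseline on.

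The definitions must be fixed before extraction. Section 8.1 provides for aggregate data only, so the restricted count cannot be recovered afterwards from what was extracted. The cost is one extra filter in an existing query and one extra row. The downside is two versions of one indicator, so reports must label which is shown.
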